Appendix 1: Schedule of assessments	18
Appendix 2: The categorization of variables	19

GLOSSARY OF ABBREVIATIONS

BASEC	Business Administration System for Ethical Committees
CI	Confidence Interval
CRF	Case report form
CTU	Clinical Trial Unit
EDC	Electronic Data Capture
EU	European Union
FAIR	Findable Accessible Interoperable Reusable
FOPH	Federal Office of Public Health
HRA	Human Research Act
HRO	Ordinance on Human
IFIK	Institute for Infectious Diseases
PFU	Plaque Forming Unit
PI	Principal Investigator
RT-PCR	Reverse Transcriptase Polymerase Chain Reaction
TLS	Transport Layer Security
WHO	World Health Organization

1 BACKGROUND AND PROJECT RATIONALE

1.1 Background

Knowledge of diagnostic tests for SARS-CoV-2 is still evolving, and their correct use and an understanding of the results is important for both clinical and epidemiological studies. Two types of diagnostic tests commonly in use for SARS-CoV-2 infections are reverse transcriptase polymerase chain reaction (RT-PCR) and anti-SARS-CoV-2-antibodies [5]. Although SARS-CoV-2 is an antigenically variable pathogen, serological surveys provide powerful evidence during a pandemic. Serological testing has an increasing role in identifying convalescent cases and persons with nonspecific mild respiratory symptoms or no symptoms who have recovered from SARS-CoV-2 without being diagnosed [6]. The current prediction is that approximately 80% to 90% of people are undocumented or asymptomatic, hence facilitating the rapid spread of the virus [7]. Because serological surveys are able to identify both asymptomatic and symptomatic cases that have passed the acute phase of COVID-19, they are paramount to generating key data on the epidemiology of SARS-CoV-2 [8,9].

The Centers for Disease Control and Prevention and others have clearly indicated the importance of seroprevalence surveys on COVID-19 [8]. Recently, several institutions have performed different types of serological surveys [10]. Results from Geneva, Switzerland, indicate a seroprevalence of 3.1% to 9.7% over 3 weeks testing [11]. Nonetheless, there are considerable differences of COVID-19 seroprevalence both within a country and between countries. A direct comparison of results is difficult because of different study types, different population selections and hence potential bias, and the use of different (mostly not validated) tests. Epidemiological antibody studies are typically categorized as (i) large-scale geographic, (ii) community-level, and (iii) special population seroprevalence surveys [8]. This project is a special population seroprevalence survey.

While the majority of exposed workers are employed in healthcare sectors, other occupational sectors also have high proportions of exposed workers [12]. A recent study suggested that protective services (e.g., police officers and others) are the third most common exposed group, after healthcare support workers and healthcare practitioners. Approximately 30% of protective services personnel are exposed to COVID-19 risk at least once per week [12].

SARS-CoV-2 is transmitted by droplets and contact (and possibly by aerosols), particularly when contact occurs over a prolonged period and in close congregation, thus providing opportunity for disease spread through droplets or fomites. For police officers who do field work, social distancing is not always possible. Police activity includes close interrogation and close contacts with various degrees of physical defence. In contrast to healthcare workers, police officers have no information on the disease condition of the other party. Previous studies have clearly shown aerosol emission of contagious organisms during speech and an increase in emission with voice loudness [13-16]. These data underscore that police officers are potentially exposed to SARS-CoV-2 during field work. This notion is even more important considering that the COVID-19 pandemic has led to social collateral effects, including domestic violence [17-20]. EU states recently reported a 60% rise in emergency calls because of domestic violence [21]. However, apart from two case reports, no data are available on COVID-19 epidemiology in protective services occupations [22,23].

1.2 Aims and Rationale

We aim to determine the immune status of the employees of the cantonal police of Bern against SARS-CoV-2 over a period of 1 year, and to investigate the risk profile of the study participants and their risk of SARS-CoV-2 exposure in their working and private environments, as well as to evaluate the use of personal protective equipment at potential exposure instances. This type of survey can help to answer important questions about risk factors for disease (person's age, location, underlying health conditions), risk of infection, and prevention of COVID-19 within this specific population. Because the age distribution of the working population may be mirrored in

this occupation, senior police officers are at risk [22]. Individuals may acquire the infection during their working hours or in the private environment, and transmit it to their colleagues at work while being asymptomatic. A police department may be further weakened by absence of personnel because of quarantine after contact with a SARS-CoV-2-PCR-positive colleague or self-isolation in the case of proven COVID-19 [22]. The acquisition of these data is paramount for future work and personnel planning of the police department. Determining how long anti-SARS-CoV-2-antibodies persist in serum following infection and which antibody titre levels are protective against reinfection will provide valuable information for the “Shield Immunity” strategy [9].

2 PROJECT OBJECTIVES AND DESIGN

2.1 Objectives and Hypothesis

- i) To determine the extent of infection in the special population of police officers of the canton Bern. We hypothesize that the COVID-19 seroprevalence within the police department will be between 1% and 2% at the beginning of the study. We further hypothesize that the seroprevalence will increase during the study period by 8% (i.e., from 2% to 10%). The rationale for this increase proportion derives from the Geneva study, and the ongoing COVID-19 pandemic till the end of study period [11].
- ii) To determine risk factors for infection by comparing the proportion of seropositivity (infected versus noninfected individuals). We hypothesize that police officers with fieldwork activity will have a higher seroprevalence than will office and administration personnel. We hypothesize that working in the city of Bern will be associated with a higher seroprevalence than will working in other geographic areas of the canton (i.e. rural area).
- iii) To monitor COVID-19 antibody titres and neutralizing capacity over time and to associate them with reinfection rates and infection-free intervals in police officers after accidental contact with a proven COVID-19 case. We hypothesize that in seropositive individuals, there will be a decreasing dynamic of antibody titres over the one-year study period, and hence, a decrease of neutralizing capacity.

2.2 Primary and secondary endpoints

Primary endpoint: The variable of primary interest is **COVID-19 seropositivity**. This variable is measured at five time points over the one-year study period. The following baseline factors may have an influence on the primary endpoint and will be obtained: (i) pre-existing comorbidities, (ii) rural versus city distribution of working place, and (iii) office work versus field work.

Secondary endpoints: We will assess the proportion of symptomatic and asymptomatic cases among seropositive participants. We will calculate the attack rate in different subgroup. These include (i) study participants with health-related risk factors (age>50 and age>60 years, diabetes, arterial hypertension, cardiovascular disease, chronic pulmonary disease, immune-compromised status due to host diseases, medical treatment, cancer, obesity), (ii) activity-related subgroups (i.e. fieldwork vs office activity), (iii) geography-related subgroups (i.e. city vs rural areas). In follow-up visits, the antibody titers (i.e. dynamic) and the neutralization capacity will be assessed. Thereby we will determine the change in serum levels of SARS-CoV-2 antibodies over time in seropositive participants.

2.3 Project design:

This is a single center special population (i.e. police officers of the canton of Bern) seroprevalence survey. It is a repeated cross-sectional investigation in the canton of Bern combined with a longitudinal cohort study with serial sampling of the included study participants. The protocol is aligned with the one of seroprevalence studies recommend by the WHO [25].

3 PROJECT POPULATION AND STUDY PROCEDURES

3.1 Project population, inclusion and exclusion criteria

The project population consists of employees working for the police department of the canton. In 2019, the police department of the canton of Bern listed 2'491 full-time equivalents [24]. In an anonymous pre-study survey performed with the police department in September 2020, 927 individuals confirmed their interest to participate to this study. Hence, we calculate with 1'000 study participants.

Inclusion criteria include all police officers of the cantonal police of Bern volunteering to participate in the study. In addition, study participants must have a valid e-mail address.

Exclusion criteria include refusal or inability to give informed consent or contraindication to venepuncture.

3.2 Recruitment, screening and informed consent procedure

Recruitment: The study will be announced through internal communication channels from the directive committee of the cantonal police of Bern (see point 11 in the BASEC application: "other documents handed over to study participants"). Within this internal communication, there will be contact details to members of the study group. In the announcement, it will be stressed that participation is voluntary. In the announcement, volunteers have the possibility to download study information and patient consent sheet. We make use of electronic media to convey the information, because the number of study participants is very high (i.e.; approximately 1'000). In addition, the study participants are not selected because of a particular disease. The majority of them will be healthy volunteers and the study purpose does not consist of sensitive health-related issues. Considering these arguments, we feel that it is justified to convey the study information electronically, and that it is unfeasible to provide the study information personally to each single study participant. The computerized system is validated within the police department (intranet). Study volunteers have the possibility to contact personally (via e-mail, telephone, zoom or skype) the study team to clarify questions or unclear issues.

Screening: Individuals fulfilling inclusion criteria are eligible for the study. This includes having a valid e-mail address.

Consent procedure: Study information and the informed consent sheet can be downloaded from the announcement on the intranet. Study participants have the possibility to contact the study team via telephone, skype or zoom to give the possibility to ask questions prior to signing the consent. Participants will also be asked to consent to store their samples in our biobank for future use (further use). The subject's consent will be documented on paper with a hand-written signature of both the patient and the investigator. Hence, patient consent sheets for participation to this study and for further use must be printed out by study volunteers, signed and sent to the study team with regular mail. The investigator will sign the consent sheets, make a copy, save the original in a folder, and send the copy back to the study participant with regular mail. No mailing costs will be burdened to study participants. The employer will be unaware of who and how many of his or her employees are participating at the time point of recruitment. No compensation or payments will be given to the project participants. Because the employer is helping to organize blood sampling, the employer will know who participated *after* study participants have been recruited. Considering the high burden of logistics, the organization for blood sampling time points by the police is needed. However, study participants have the possibility to organize the blood sampling via the study team (and not via the police), if they wish. The employer will not be aware of any individual result.

Efforts to ascertain voluntary participation: In the (i) pre-study survey, (ii) announcement, and (iii) study information, it will be stressed that participation in the investigation is voluntary and that the participant is free to withdraw (without justification) from the investigation at any time without consequences and without affecting professional responsibilities. The directors of

the police department are only authorized to view high-level summary information about the survey results, but will not be able to track an individual's result or decision to participate in or withdraw from the study. Study participants can choose the location for blood sampling when making an appointment in the given time frame, i.e., police station versus Interregionale Blutspende SRK. Similarly, the study participation requires a computer with internet access to fill out the questionnaire. Participants can fulfill this task at a location of their choice.

3.3 Study procedures

The overall project will span an 18-month period. We anticipate starting the study in December 2020, with a baseline visit and first sampling in January 2021. Sample collection will be terminated in February/March 2022. Hence, the project duration for each study participant will be 1 year.

The study protocol is aligned with that of the WHO for population-based age-stratified sero-epidemiological investigations. We adapted the protocol for our specific population and for the geographic region of the canton of Bern [25]. Data and serum results will be collected in a standardized format according to the questionnaires and tools in the WHO protocol to assist with data harmonization and comparison of results.

Upon signed consent, each study participant will be assigned a study identification number (code) for the labelling of questionnaires and serum specimens.

Each participant recruited for the investigation will be asked to complete an online questionnaire at their convenience within time frame of 2 to 3 weeks, which covers information on demographics and possible COVID-19 exposure or infection (see point 5 in the BASEC application: "CASE REPORT FORM"). Returned questionnaires will be reviewed for completeness and responses electronically stored in a database (REDCap).

A serum sample will be collected from each participant upon recruitment into the investigation (visit 1, baseline). According to the study participant's preference, the study team will conduct police station visits to collect specimens OR study participants will visit the Interregionale Blutspende SRK for blood sampling. Serial sampling is then to be conducted every 3 months (i.e., five sampling time points over 1 year), meaning that each participant will be asked to attend a total of 4 follow-up visits.

Figure 1 describes when data and specimens will be collected according to the study plan permitted timeframe for each visit. A visit corresponds to one blood sampling appointment. A visit is defined as a time frame between 2 and a maximum of 3 weeks. Dates for appointments will be randomly alternated between police stations in cities and those in rural areas to preserve equal temporal distribution of visits between these areas. Results from microbiological analyses will be entered into REDCap. A schedule of assessments is also illustrated in appendix 1.

[figure not shown]

Figure 1: Schematic overview of the study procedure

Each sample will be labelled with the study participant's code immediately prior to blood withdrawal. For each serum sample collected, the time of collection, the conditions for transportation, and the time of arrival at the study laboratory will be recorded. Given the efficient means of transport in the canton of Bern, we anticipate that serum samples will reach the laboratory within the same day after collection. They will be aliquoted and stored at our at the Interregionale Blutspende SRK (-30°C), for coordinated analysis of batches. The diagnostic laboratories of both the Interregionale Blutspende SRK and the IFIG have the required government permits to operate a diagnostic service for clinical specimens of human origin, including storage of such specimens; furthermore, they are accredited to the ISO/IEC 17025 Standard.

On each sample two commercially available SARS-CoV-2 serological assays will be performed (Elecsys® Anti-SARS-CoV-2-Test). According to the manufacturer's information, the specificity is 99.81 % (95% CI 99.65 – 99.91 %) and sensitivity 100 % (88.1 – 100 %), respectively. The rationale for using this particular test includes a performance evaluation at the Interregionale Blutspende SRK that demonstrated a high specificity (Riester et al. medRxiv 2020.08.07.20169987). Overall specificities for the Elecsys Anti-SARS-CoV-2 immunoassay in 9575 samples from blood donors (n = 6714) and routine diagnostic testing specimens (n = 2861) were 99.82% (95% CI 99.69-99.91) and 99.93% (95% CI 99.75-99.99), respectively. In addition, the test will be purchased to a reasonable price. The rationale for choosing two commercially available SARS-CoV-2 serological assays is the following. One test detects anti-nucleocapsid antibodies, while the other detects anti-spikeprotein antibodies. Anti-nucleocapsid antibodies detect antibodies derived from natural infection but do not detect antibodies derived from mRNA-vaccination. It is important for both the investigator and the study participant to identify antibodies derived from vaccination. Therefore, we complement the tests for anti-nucleocapsid antibodies with tests for anti-spike-protein antibodies. Testing will be carried out at the Interregionale Blutspende SRK.

In serum samples with positive antibody test, quantification of neutralizing antibodies will be performed at the IFIG. They will be measured by pre-incubating serial dilutions of baseline and convalescent serum with 200 to 400 plaque forming units (PFU) of SARS-CoV-2, after which a PFU reduction assay will be performed on Vero-E6 cells. After 2 days, cells will be fixed and stained with crystal violet to analyse the neutralizing capacity of antibodies generated towards SARS-CoV-2, as previously described [26].

The results of Anti-SARS-CoV-2-Test of will be communicated to study participant via e-mail within 2 weeks of blood sampling. The results of neutralization capacity will be communicated at the end of the study period. This experimental assay will be performed in the research laboratory with all positive samples during one month, at the end of the study period.

Seropositive participants or participants with a positive SARS-CoV-2 test in the past (PCR or antigen test) will be asked to complete an additional questionnaire that investigates possible contacts (i.e., working versus private environment) and sources of transmission (see point 5 in the BASEC application: "CASE REPORT FORM").

Seropositive participants or vaccinated participants will be contacted by the study team within 4 weeks after laboratory result, for one additional blood sampling that investigates neutralization capacity. Seropositive participants with vaccination will be contacted twice. Figure 2 illustrates the sampling scheme.

Antibodies	Vaccine	No. of blood sampling in 1 year
		
negative	no	5 baseline + every 3 months
positive	no	6 baseline + every 3 months + 1 sampling
negative	yes	6 baseline + every 3 months + 1 sampling
positive	yes	7 baseline + every 3 months + 2 samplings

Figure 2: Schematic overview of the blood sampling over one year

Measures taken to reduce expected biases: If study participants reveal anti-SARS-CoV-2-antibodies at baseline or reveal seroconversion during the study year, additional investigations will be performed. Serum sampling will be repeated 2 and 4 weeks after the first positive antibody test result to confirm seropositivity and to exclude false positive results. It is possible that among the study participants, scientifically motivated persons or individuals keen to know their serostatus will in particular volunteer to donate samples. Such a scenario points towards a convenience sampling, and has a higher uncertainty bias in comparison to random samples. We will try to counterbalance this potential bias by including a large sample size (i.e., high proportion of the total number of employees) and by monitoring the age distribution during recruitment. Another potential bias includes the social pressure from superiors or peers to participate. We have included the following counter measures: First, there is no possibility for superiors to identify participating employees at the time of recruitment if study volunteers sign consent in their private area. Second, the online questionnaire will directly ask participants. Third, study participants can choose the location for blood sampling when making an appointment in the given time frame, i.e., police station versus Interregionale Blutspende SRK. In the latter location, privacy can be guaranteed, whereas in the former location, working colleagues will be aware of blood sampling, and hence, study participation.

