At every visit, we will first calculate the crude seroprevalence as the proportion of the seropositive samples among all collected samples. Second, we will adjust the seroprevalence for test characteristics (false positive and false negative rate). Third, we will calculate the weighted seroprevalence to adjust for sampling imbalances, with weighting factors based on the demographic structure of the police force (age, sex, rural vs. city distribution). We will furthermore analyze changes in seropositivity in a repeated-measures mixed-effects logistic regression model. In a second step, we will include health-related, activity-related and geography-related risk factors as covariates into the model to study effects of these factors and derive corresponding odds ratios. Change of risk factors over time will be accounted for. The change of antibody titres over time will also be analyzed using mixed models.

In addition to demographic characteristics, a descriptive analysis of health-related variables (i.e. diabetes, arterial hypertension, cardiovascular disease, chronic pulmonary disease, immunocompromised status because of host diseases or medical treatment, cancer, obesity), and activity-related data (i.e. fieldwork activity vs office and administration activity, working in cities or rural areas) will be performed. The categorization of variables is illustrated in appendix 2. Comparison of categorical and continuous variables will be performed with chi-square tests, t-tests, Wilcoxon-Mann-Whitney-Test, Kruskal-Wallis-Test and multivariate analysis, accordingly. The significance level will be two-sided $\alpha = 0.05$.

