All data entered into the CRFs are transferred to the database using Transport Layer Security (TLS) encryption. Each data point has attributes attached to it identifying the user who entered it with the exact time and date. Retrospective alterations of data in the database are recorded in an audit table. Time, table, data field and altered value, and the person are recorded (audit trail). A multi-level back-up system is implemented. Back-ups of the whole system including the database are run internally several times per day and on external tapes once a day. The back-up tapes are stored in a secure place in a different building.

Coding: Each study participant will be assigned a unique study identification number (barcode) for the labelling of questionnaires and serum specimens. We will use a barcode system that allows scanning and printing out stickers. This barcode will be coupled with a second code that indicates the visit number and the result assignment. Study-related data of the patient will be collected in a coded manner. The names of the patients will not be disclosed. As outlined above, e-mail addresses provided by the study participants will be used. Depending on the provided e-mail address, the patient's names may be identifiable. After termination of the study, and confirmation of completeness of data, e-mail addresses will be removed, and only coded data used.

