Appendix 2: The categorization of variables

Parameter	Definition	Source of data to calculate the parameters
Cumulative incidence	The proportion of individuals with seropositivity	Laboratory result
Age- and gender specific attack rate	The proportion of individuals per age and gender strata with seropositivity	Laboratory result Questionnaire
Symptomatic proportion of cases	The proportion of individuals with seropositivity who showed symptoms or signs of COVID-19 infection (+/- confirmed PCR result in the past)	Questionnaire
Asymptomatic proportion of cases	The proportion of individuals with seropositivity who showed no symptoms or signs of COVID-19	Questionnaire
Attack rate in risk group (health-related data) (Persons over 65 years are not included because retirement is expected at this age in the study population).	Study participants with one or more of the following risk factors: diabetes, arterial hypertension, cardiovascular disease, chronic pulmonary disease, immuno-compromised because of host diseases or because of medical treatment, cancer, obesity (BMI > 30 kg/m ²)	Laboratory result Questionnaire
Activity related cumulative incidence	The proportion of individuals with seropositivity in the following 2 groups: Group 1: Police officers with fieldwork activity and frequent population contact. Group 2: office and administration occupation with low population contact.	Laboratory result Questionnaire
Geography related cumulative incidence	The proportion of individuals with seropositivity in the following 2 groups: Group 1: occupation in cities (Bern, Thun, Biel) Group 2: occupation in rural area of Bern or in cities but not belonging to group 1.	Laboratory result Questionnaire
Sub-study in seropositive study participants		
Parameter	Definition	Source of data to calculate the parameters
Serological response to infection	The change in serum level of specific antibodies to COVID-19 virus (increase in antibody titres)	Laboratory result over time
Seropositive result confirmation (specificity)	Seropositive result at baseline or seroconversion during the study year that will be confirmed with two additional serum samples, two and four weeks after the positive antibody result.	Laboratory result
Work or social environment-related exposure	Study participants perception of possible COVID-19 exposure	Questionnaire

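### Some questionnaires may be answered after the serology result is known, which mainly exposes the symptomatic share and self-reported contact frequency and is cheap to guard against

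*Combined protocol and SAP*

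**What the plan says.** Section 3.3 sets two clocks. Participants are asked to "complete an online questionnaire at their convenience within time frame of 2 to 3 weeks". The antibody results "will be communicated to study participant via e-mail within 2 weeks of blood sampling". The first clock has no stated starting point and the second has no minimum delay. Baseline serum is drawn at recruitment, and for visits in general "A visit is defined as a time frame between 2 and a maximum of 3 weeks". Appendix 1 puts questionnaire and blood sampling in the same visit column without ordering them.

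The questionnaire "covers information on demographics and possible COVID-19 exposure or infection". Appendix 2 names a questionnaire as the source for the symptomatic and asymptomatic proportions, for perceived exposure and, with the laboratory result, for the activity groups. The first activity group is "Police officers with fieldwork activity and frequent population contact". In section 4.1 the sponsor states that "we will include health-related, activity-related and geography-related risk factors as covariates into the model", from which odds ratios are derived.

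The bias paragraph of section 3.3 deals with false positives, volunteer bias and social pressure. It does not mention answers given with the result known. Sections 4.2 and 7.1 have staff follow up missing answers, with no limit relative to result release. Section 7.3 says of the database: "Each data point has attributes attached to it identifying the user who entered it with the exact time and date". No planned analysis uses that time stamp to compare answer time with result time.

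**The concern.** A participant who has just been told of a positive result has a reason to search memory for symptoms and contacts that a participant told of a negative result does not have. If the questionnaire can be completed after release, reporting may depend on the outcome.

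Two results are exposed. The symptomatic proportion is calculated among seropositives only, so extra recall by informed positives raises it directly. The activity comparison under objective ii depends partly on how often participants say they meet the public; if informed positives report more contact, the odds ratio moves away from 1 without any true effect. The mixed model has no term that corrects reporting that differs by serostatus. The order in which answers and results arrived cannot be changed once the data are collected.

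**Working it through.** The plan states no figure on this point, so there is none to reproduce. The check covers whether the two windows can overlap and how much that could matter.

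**Step 1. Overlap for one participant, both clocks counted from the draw.** Overlap = max(0, questionnaire window − day of result). The windows of 14 and 21 days and the day-14 limit are from section 3.3; day 7 is an assumed earlier release.

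| Questionnaire window | Result on day 14 | Result on day 7 |
|---|---|---|
| 14 days | 0 days | 7 days |
| 21 days | 7 days (7/21 = 33%) | 14 days (14/21 = 67%) |

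**Step 2. Share answering after the result in a shared visit window.** Assume draws and answers are independent and uniform over one shared 21-day window.

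- Result 14 days after the draw: (7/21)²/2 = 5.6%.
- Result 7 days after the draw: (14/21)²/2 = 22.2%.

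The one-third case corresponds to 7/21 in step 1, where each person's questionnaire clock starts at his or her own draw.

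**Step 3. Spurious odds ratio when the true one is 1.** Assumptions, none of them in the documents: 30% truly exposed regardless of serostatus; uninformed participants report with 80% sensitivity and 5% false reports; informed positives report with 90% sensitivity and 5% to 10% false reports; negatives do not change.

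- Negatives and uninformed positives: 0.30 × 0.80 + 0.70 × 0.05 = 27.5%.
- Informed positives: 0.30 × 0.90 + 0.70 × 0.05 = 30.5%, or with 10% false reports 0.30 × 0.90 + 0.70 × 0.10 = 34.0%.
- With a share f informed, positives report 27.5% + f × (3.0 to 6.5 points). The odds in negatives are 0.275/0.725 = 0.379.

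| f | Reported exposure in positives | Spurious odds ratio |
|---|---|---|
| 5.6% | 27.7% to 27.9% | 1.01 to 1.02 |
| 22.2% | 28.2% to 28.9% | 1.03 to 1.07 |
| 33.3% | 28.5% to 29.7% | 1.05 to 1.11 |

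**Step 4. Symptomatic share.** If the same assumed rates held for symptoms, the reported share among positives would rise by f × (3.0 to 6.5 points): 0.2 to 0.4 points at 5.6%, 0.7 to 1.4 at 22.2%, and 1.0 to 2.2 at one third.

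**Step 5. Dependence on the reporting assumption.** In a second model, a share r of truly unexposed informed positives report exposure, so reported exposure in positives is e + (1 − e) × f × r. With e of 0.3 to 0.5 and r of 0.1 to 0.3, the spurious odds ratio is 1.02 to 1.10 at f = 10% and 1.05 to 1.27 at f = 25%. The size therefore depends on assumptions that the documents cannot settle.

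**Step 6. Comparison with sampling error.** With 1,000 participants and 27.5% reporting exposure, the standard error of the log odds ratio is √[(1/n₁ + 1/n₀)/(0.275 × 0.725)].

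- At 2% seroprevalence (20 positives, 980 negatives) it is 0.506, and the 95% limits lie a factor exp(1.96 × 0.506) = 2.7 either side.
- At 10% (100 and 900) it is 0.236, a factor of 1.6.

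The shifts in step 3 are well inside both.

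**The case against.** The strongest reply is that the overlap is possible but not established. The start of the questionnaire window is not stated, and Figure 1, which is said to show the timing, is not available here. Section 3.3 describes consent, then questionnaire, then serum, which fits a link sent before the draw as well as one sent after it. With a 14-day window and a day-14 result there is no overlap, and storing samples for batch analysis argues against very early results. This stands: the windows may overlap, and no more can be said.

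A reader might infer that the risk-factor odds ratios are inflated in general. The documents do not support that. The listed covariates are mostly factual: diagnoses, BMI, fieldwork versus office, named cities versus rural. Job type or diabetes is unlikely to be reported differently because of a blood result. Protective equipment is not a listed covariate, and contact enters only through the wording of the activity groups. Detailed contact and source questions belong to the additional questionnaire, which goes by design to people who already know of a positive result or past test.

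A reader might also apply the reporting rates of step 3 to a case where everyone answers after the result, which gives odds ratios of 1.16 to 1.36. That does not fit a partial overlap.

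Finally, participants know earlier results at visits 2 to 5, and some know a past PCR or antigen result at baseline, so answers given before release are not fully blind. This stands, but it does not empty the remedy. Baseline answers would be protected from the serology result. Before a first seroconversion, participants without a past positive test hold only negative study results, whether or not they are about to convert.

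**Conclusion.** The point holds in a limited form. The visible text lets the questionnaire follow the result, contains no safeguard and plans no analysis by answer time. The exposed results are the symptomatic and asymptomatic proportions and the self-reported contact part of the activity grouping.

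Under the reporting rates assumed in step 3, the spurious odds ratio is about 1.01 to 1.07 if 6% to 22% answer after the result, and 1.05 to 1.11 if one third do. It could be larger if informed positives over-report more, and it is zero if every questionnaire precedes release. These shifts are small against the expected precision and do not threaten the seroprevalence estimate, which comes from the laboratory. This is a cheap improvement to a secondary endpoint and one risk-factor comparison, not a flaw that undermines the study.

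**What to change.** 1. In section 3.3, state when the questionnaire window opens, and time the automated REDCap invitation and reminder so that the questionnaire is requested before or at the blood draw at every visit. Still accept late questionnaires, and do not hold back results.
2. Record the result-release time and use the existing time stamp to flag each answer given or changed after release, including answers obtained through missing-data queries.
3. Keep all available data as the main analysis, in line with section 4.2. Add one sensitivity analysis of the symptom and activity/contact results limited to answers given before release. Making that restriction the main analysis would favour prompt responders and discard scarce positives: of about 20 at baseline (2% of 1,000), some 1 to 4 would go at 6% to 22% late and about 7 at one third.
4. State in the bias paragraph that this addresses only the current visit's result, not knowledge of earlier visit results or past PCR or antigen tests.

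The cost is a small change to the invitation schedule, one flag variable and one extra analysis. No additional visits or samples are needed.
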